- 1.6 *Does EAA influence markers of mitochondria function vs. Placebo?*
- 1.7 *Does statin use influence cell respiration over time?*
- 1.8 *Does EAA affect primary cell derived myocyte function over time?*
- **Specific Aim #2 (Physiology): Determine if short-term prevention of atrophy, weakness, and functional mobility leads to positive changes in muscle cell structure and function, and quality of life in the long term (6 months post-TKA) vs. Placebo.**
Successful completion of Aim 2 will identify a role for EAA supplementation in clinical settings using a mechanistic approach. Our approach is based on strong preliminary clinical data from older men and women following TKA demonstrating that EAA supplementation for 1 week prior to, and for 2 week post-TKA was effective in preventing significant muscle atrophy (37). However, our preliminary data suggest that in the EAA group, atrophy at 2 weeks post-TKA was half that at 6 weeks in the operative quadriceps and hamstrings. This potential 'catch-up' muscle loss was not observed in the non-operative leg within the EAA group but was identical to the change from 2 weeks to 6 weeks in the operative leg of the Placebo group. We interpret these data to support the need to supplement for 6 weeks post-TKA in order to maximally prevent bilateral muscle atrophy.

The proposed research design will answer the following questions:

- 2.1 *Does EAA prevent short-term (7 wk post-TKA) bilateral muscle atrophy, preserve quadriceps strength, and accelerate the return of functional mobility vs. Placebo?*
- 2.2 *Are there short-term sex differences on the above outcome measures?*
- 2.3 *Will EAA increase long-term (6 mo post-TKA) quadriceps functional mobility vs. Placebo?*
- 2.4 *Does EAA improve longer-term (6 mo post-TKA) functional mobility and measures of quality of life vs. Placebo?*
- 2.5 *Are there long-term sex differences in functional mobility or measures of quality of life?*
- 2.6 *Does inhibition of angiogenic factors (IFG-1 & VEGF) inhibit a pro-angiogenic response?*
- 2.7 *Does EAA influence markers of inflammation vs. Placebo?*
- 2.8 *Does EAA influence markers of mitochondrial function vs. Placebo?*
- 2.9 *Does statin use influence cell respiration over time?*
- 2.10 *Does EAA affect primary cell derived myocyte function over time?*

Methods, Materials and Analysis

Study Design.

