Prospective, randomized, blinded, controlled, two-arm, parallel clinical trial design with 1:1 allocation ratio to EAA versus Placebo. Staged enrollment is planned; we will complete Aim #1 before enrolling into Aim #2.

Investigational Supplement.

This trial is being conducted under IND#121601, with mandates to report results from Aim #1 to the Food and Drug Administration (FDA). The investigational supplement (or Placebo) will be ingested twice-daily, at 10:00a and 2:00p for one week prior to TKA surgery.

- Aim 1 -Supplement will be compounded by Northwest Compounds, and ordered per standard of care for pharmaceutical ordering (fax or phone call) and dispensing.
- Aim 2 – Supplement will be supplied by MEND Nutrition, Inc. Supplement will come individual containers shipped directly to the [name] Lab. Containers will be distributed to patients by study coordinators. Patient will measure two (2) scoops per dose (twice daily). Scoop provided in each container.

Aim 1 Supplement will be suspended on the day of surgery and resume on post-operative day #1. On post-operative days where subject participates in physical therapy, supplementation will occur within one hour of treatment (20 g of EAA or Placebo). The EAA supplement or Placebo composition is described in Table 1 below. Our preliminary study suggest the EAA supplementation is safe and no subjects withdrew due to problems with supplement ingestion (37).

Aim 2 Supplement will be suspended on the day of surgery and resume on post-operative day #1. On post-operative days where subject participates in physical therapy, supplementation will occur within one hour of treatment (23.42 g of EAA or Placebo). The EAA supplement or Placebo composition provided by MEND Nutrition, Inc. is described in Table 2 below. Our preliminary study suggest the EAA supplementation is safe and no subjects withdrew due to problems with supplement ingestion (37). Supplement composition has changed due to new manufacturer/supplier of the supplement (MEND). To our knowledge there are no scientific or risk implications related to the change in proportions.

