Gene Expression: RNA will be extracted from 15-20 mg of muscle tissue according to protocol (Molecular Research Center, Inc, Cincinnati, OH). High quality RNA will be determined using lab-on-chip microfluidic technology automated nucleic acid electrophoresis and analysis. Total RNA will be reverse transcribed into cDNA using the iScript cDNA Synthesis Kit (Bio Rad, Hercules, CA) on a C1000 Thermal Cycler (Bio Rad, Hercules, CA). Determination of relative mRNA expression will be performed using a CFX96 Real-Time System coupled to a C1000 Thermal Cycler (Bio Rad, Hercules, CA) and Genomics Core facility NextSeq 500 at the University of Oregon.

Mitochondrial respiration. Oxidative phosphorylation rates in response to 50 μ M ADP will be determined in saponin permeabilized vastus lateralis biopsies (5-10 mg) using the two-channel high resolution respirometer (Oroboros Oxygraph; Innsbruck, Austria) with the saturating concentrations of the following substrate combinations [in mM]: pyruvate [5] + malate [5], palmitoylcarnitine [0.04] + malate [5], succinate [10] + 100 nM rotenone, or malate [5] + glutamate [10]. Respiration studies were performed at an initial oxygen concentration of 300 μ M at 37°C in MiR06 respiration buffer containing [in mM] EGTA [0.5], MgCl₂·6 H₂O [3], K-lactobionate [60], taurine [20], KH₂PO₄ [10], HEPES [20], sucrose [110], 1g/L BSA, 280U/ml catalase, pH 7.4 [with KOH].

Mitochondrial dysfunction may introduce sample bias as well as negatively impact short and longer-term function. To account for this, we propose to measure mitochondrial respiration using the Oroboros O2k respirometer, and normalize results statistically and use the non-operative leg as internal control.

Secondary Outcome Measures. Study Aim #1 will allow the team to collect preliminary functional outcome data to better inform the long-term study (Aim #2). The secondary outcome measures will be quantified using the following study activities and procedures:

- **Muscle volume.** The MRI unit is located at the Lewis Center for Neuroimaging (LCNI) on the University of Oregon campus. Should the MRI unit at LCNI be unavailable within study-specific assessment points (i.e. scheduling or mechanical issues), the MRI at the Slocum Center for Orthopedics will be utilized. In addition, patients in partnership with the study team, may elect to have all scans performed at the Slocum Center.

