Power analyses. For our power calculations, we have assumed a Type I error rate (α) of $.05$, two-tailed. We based power calculations on effect sizes (d) that we derived from analysis of preliminary data preliminary data and prior studies (10, 30, 32, 33, 36, 41, 51, 113). We calculated d as the standardized mean difference between treatment conditions at follow-up: $d = (x_C - x_T)/S$, where x_C represents the primary outcome mean in the Placebo and EAA conditions and S is the pooled standard deviation, after adjusting x for pretest scores and covariates (sex, tourniquet time, age, body mass index, fat/carbohydrate/protein intake).

We propose to enroll **40 total subjects for Aim 1** who are retained through protocol completion (20/group, EAA and Placebo, randomized to either 1 week or 2 week post-operative biopsies), and **80 total subjects** (40/group, EAA and Placebo) **for Aim 2** who are retained through protocol completion to account for possible attrition and to ensure sufficient power to test the hypotheses that EAA therapy up-regulates basal levels of muscle protein synthesis, and reduces post-operative atrophy bilaterally, preserves quadriceps strength, and improves functional mobility relative to a Placebo condition.

Effect sizes. Effect sizes were as follows: (a) Cell and FSR data: REDD1 $d = 1.24$, SLC36A2 $d = 1.27$, and FSR $d = 1.51$ (FSR calculated from mean change from baseline). The mean effect across outcomes was $d = 1.37$, reflecting large effects. (b) Physiological and functional data (percent change from Baseline to 6 wk): operative quadriceps volume $d = 1.52$, and isometric strength $d = .90$; non-operative quadriceps volume $d = 1.05$, and isometric strength $d = .66$; timed up-and-go test $d = 1.03$, timed stair ascent $d = 1.08$, timed stair descent $d = 1.13$, and six-minute walk test $d = .70$. Mean effect size was $d = 1.01$, reflecting large effects.

Power calculations. Power calculations were based on the sample size and minimally detectable ES (MDES) as follows:

- **Aim #1:** For a sample size of 20 completed subjects/group (10/group for metabolic studies, however, EAA vs. Placebo = 20 total EAA and 20 total Placebo). Aim 1, proposed study can detect

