ESs of $d > 1.10$ with 85% power, assuming no pretest covariate, and the minimally detectable ES drops to 0.95 or 0.72 with pretest covariates of $r = .50$ or $.75$, respectively. The preliminary results show ESs averaged 1.37 for Cell and FSR outcomes, and all exceeded .95. The proposed study would thus have the power to detect anticipated condition effects for Cell and FSR outcomes in Aim 1 with 10 subjects per condition. We can also detect moderation effects for sex if the associated interaction accounts for at least 21% to 31% of the variance, assuming covariate of $r = .75$ or $.50$, respectively.

- **Aim #2:** For a sample size of 40 completed subjects/group (EAA and Placebo), the proposed study can detect ESs of $d > .79$ with 85% power, and the minimally detectable ES drops to .68 or .52 with pretest covariates of $r = .50$ or $.75$, respectively. Preliminary results show an average ES of $d = 1.01$ across all Aim 2 outcomes, so this study will have power to detect anticipated physiological and functional effects with 40 subjects per condition. We can detect condition-by-sex moderation effects if the associated interaction accounts for at least 12% to 19% of the variance, assuming covariate of $r = .75$ or $.50$, respectively. The tests of sex-by-condition interactions in both aims are likely underpowered for some important effects, so we will also consider the size of the effect, even if not statistically significant, as an indicator of potentially important sex-related differences.

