Potential Research Benefits to Participants

The proposed research is based on strong preliminary evidence that EAA reduce post-operative muscle atrophy by 3-fold in the operative and non-operative lower extremities. Further in our pilot studies,

these positive results extended to gains in strength in the non-operative quadriceps—important for long-term ability to normalize function, and to accelerated recovery of functional mobility (stair descent). These data are all derived from older adults. Preserving quadriceps strength is clinically important because poor strength is directly linked to reduced physical function and gait. Quadriceps weakness inhibits balance (84), reduces functional mobility (20, 82), and increases the risk of falls (83) in older adults. Our preliminary data suggest that patients on EAA treatment lost less muscle from their extremities compared to subjects on placebo. An additional potential benefit will be our potential to provide physical therapy to patients without insurance or in instances where the subjects insurance does not pay for the total number of visits we require for this study. These may be considered a potential benefit.

We repeated this study with 39 patients in 2014-2016 and again found the group taking EAA lost less muscle than the placebo group.

Investigator Experience

University of Oregon

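### The Aim 2 power claim rests on 6-week pilot effects, so power for the aim's 6-month questions is unsupported

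*Combined protocol and SAP*

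**What the plan says.** In the combined protocol and SAP, the Data Analysis section takes a minimally detectable effect size (MDES) for Aim 2 and compares it with pilot effects.

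- **Detectable effect (Power calculations, Aim #2).** With 40 completers per group and 85% power, the stated MDES is .79, falling to .68 or .52 with a pretest correlation of .50 or .75.
- **Anticipated effect (same paragraph).** The pilot average is d = 1.01 across all Aim 2 outcomes, and the paragraph concludes: "so this study will have power to detect anticipated physiological and functional effects with 40 subjects per condition".
- **Where 1.01 comes from (Effect sizes).** The eight values behind it are headed "Physiological and functional data (percent change from Baseline to 6 wk".
- **What the aim asks (Specific Aims).** The Aim 2 statement is about the long term, 6 months after surgery. Question 2.4 reads: "Does EAA improve longer-term (6 mo post-TKA) functional mobility and measures of quality of life vs. Placebo". Question 2.3 also names 6 months and question 2.5 is long-term. Questions 2.1 and 2.2 are short-term, with 2.1 set at 7 weeks.
- **Follow-up and treatment.** The Aim 2 primary outcomes are followed for 6 months (Primary Physiological Outcome Measures). The supplement runs from one week before to six weeks after surgery (Project Summary).
- **Role of Aim 1 (Secondary Outcome Measures).** "Study Aim #1 will allow the team to collect preliminary functional outcome data to better inform the long-term study (Aim #2".

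**The concern.** The power sentence carries no time limit, so it reads as covering the 6-month questions. The effect it relies on was seen only at 6 weeks. Whether an early gain lasts is the hypothesis of Aim 2, so it cannot also serve, unstated, as the basis for the power.

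The plan itself gives reason for caution. Question 2.1 speaks of accelerating the return of mobility, and arms that differ in speed of recovery can separate early and converge later. The Aim 2 rationale also reports catch-up muscle loss in the operative leg of the EAA group between 2 and 6 weeks.

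What is at stake is how a null 6-month result is read. Next to an unqualified claim of adequate power, it could pass as evidence of no lasting benefit when it may only be uninformative.

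**Working it through.** **Inputs.** From Power analyses: "we have assumed a Type I error rate (α) of $.05$, two-tailed". From Power calculations, Aim #2: "For a sample size of 40 completed subjects/group (EAA and Placebo"). From Study Design: "two-arm, parallel clinical trial design with 1:1 allocation ratio to EAA versus Placebo". SD is set to 1, so effects are in SD units.

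**1. The pilot average reproduces.** (1.52 + .90 + 1.05 + .66 + 1.03 + 1.08 + 1.13 + .70) / 8 = 8.07 / 8 = 1.009, stated as 1.01. Five of the eight (two quadriceps volumes, two isometric strengths, six-minute walk) are on the list of procedures omitted from the current Aim 2. The three kept tests are timed up-and-go, stair ascent and stair descent: (1.03 + 1.08 + 1.13) / 3 = 1.08, also at 6 weeks.

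**2. The stated MDES does not reproduce at 40 per group.** MDES = (z.975 + z.85) × √(2/n), multiplied by √(1 − r²) for a pretest covariate, and checked with the noncentral t. At n = 40 the normal formula gives (1.960 + 1.036) × √(2/40) = .67.

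| | r = 0 | r = .50 | r = .75 |
|---|---|---|---|
| Stated in the plan | .79 | .68 | .52 |
| Noncentral t, 40 per group | .68 | .59 | .45 |
| Noncentral t, 30 per group | .79 | .68 | .52 |

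The stated figures match about 30 per group, although the text says 40 completed. They are conservative: at 40 per group, d = .79 without a covariate has 94% power, not 85%.

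**3. Power at 40 per group.** Noncentral t with effective size d/√(1 − r²). The documents give no 6-month effect, so the share of the 6-week effect that remains is an assumption. The lower rows round the average to 1.0.

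| Effect at 6 months | r = 0 | r = .50 | r = .75 |
|---|---|---|---|
| All remains, d = 1.01 | 99.4% | 99.9% | >99.9% |
| Half remains, d = .50 | 60% | 72% | 92% |
| A quarter remains, d = .25 | 20% | 25% | 39% |

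**4. Share that must remain for 85% power.** MDES / 1.01. By the plan's figures: .79/1.01 = 78%, .68/1.01 = 67%, .52/1.01 = 51%. By the recomputed figures for 40 per group: 67%, 58% and 44%.

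**5. Time off supplement.** Six months is about 26 weeks, and 26 − 6 = 20 weeks between the last dose and the 6-month visit.

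**Caveat on scale.** Power analyses defines d as a follow-up difference already adjusted for pretest and covariates, while Effect sizes lists percent changes. If d is already adjusted, dividing by √(1 − r²) adjusts twice, and the r = .50 and r = .75 columns in step 3 do not apply.

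**The case against.** A reader might infer that Aim 2 is underpowered at 6 months, or that its stated power is simply false there. The documents do not support either. The MDES is tied to no time point and holds at 6 months if 40 per group complete. Only the comparison with d = 1.01 fails. With half the effect left and r = .75, power is still 92%.

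The plan can also point to four things.

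- **Short-term questions.** Questions 2.1 and 2.2 roughly fit a 6-week pilot effect. This stands, and the claim can stay for 6-week outcomes.
- **Reasons to expect persistence.** The Introduction links early function to later recovery. The cited pilot supplemented only to 2 weeks after surgery, so if the 6-week effects come from it, they were measured about 4 weeks after the last dose. That is some sign of persistence, but the catch-up loss points the other way and neither reaches 6 months. The Introduction's remark that function peaks at 6 months describes patients in general, not the gap between arms.
- **The longitudinal model.** Random coefficients analysis over five functional assessments may be more powerful than the single-visit comparison used here. The plan gives no power figure for it, and it would still need an assumed 6-month effect.
- **Completed data.** One might expect Aim 1 to close the gap. Potential Research Benefits says "We repeated this study with 39 patients in 2014-2016", without calling it Aim 1 and reporting only muscle loss. Aim 1 follow-up ends at 6 weeks. It also used another formulation (20 g with 3.6 g leucine, against 23.42 g with 7.4 g) and another age range (50–80, against 40–80). It cannot supply a 6-month effect or correlation.

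**Conclusion.** The concern holds for the long-term questions. The power sentence compares a detectable difference with an effect measured only at 6 weeks and applies the result to all Aim 2 outcomes, although five of the eight pilot outcomes behind the average are no longer measured and the aim runs to 6 months. Nothing in the documents bridges the two time points.

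The size of the problem depends on the unknown retained share: power runs from 20% to 92% across the half and quarter scenarios. These figures assume 40 completers per group, a single-visit comparison and, in the covariate columns, a d not already adjusted for pretest. How a null result would be read is a judgement, since the plan does not say.

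**What to change.** Reword the Aim 2 power paragraph.

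- **6 weeks.** Limit the statement that the study will have power to the pilot functional tests still measured in Aim 2: timed up-and-go, stair ascent and stair descent, mean d = 1.08. State whether d is pretest-adjusted.
- **6 months.** Give only the detectable difference at 85% power with the n used: .68, .59 or .45 SD for r = 0, .50 or .75 at 40 completers per group. Note that the present .79, .68 and .52 correspond to about 30 per group. Say that no 6-month effect estimate or baseline-to-6-month correlation supports the calculation.
- **Reporting.** Commit to giving the 6-month contrast with its confidence interval, so that a null is not taken as evidence of no lasting benefit.
- **Aim 1 data.** They may be used to check the 6-week inputs only, with the different formulation and age range noted.

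The cost is one rewritten paragraph and, if wanted, one re-run of the 6-week inputs on completed data. No patients or visits are added. The detectable difference looks better than the one now stated, while the power claim becomes narrower.

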Randomization Assignments. Aim #1 will consist of 2 groups (N=20/group through protocol completion; EAA vs. Placebo) that are identical in protocol design except for metabolic studies.

Metabolic studies will partition the EAA group into 2 (post-TKA bilateral biopsy at 1 or 2 weeks after

UO IRB Protocol #12272013.024 PeaceHealth Protocol #551187

January 2019

Research
 Compliance Services
 Page | 11
 01/26/2019-11/06/2019

"APPROVED"

surgery) and Placebo group into 2 (post-TKA bilateral biopsy at 1 or 2 weeks after surgery). This will allow us to collapse data by group treatment group; questionnaire, activity, food-log, strength & activation, muscle volume and functional data (this equals N of 20 through protocol completion for EAA and N of 20 for Placebo through protocol completion; 20/group, enough for sex comparison), while enabling us to quantify changes over time in metabolism (D_2O) and at discrete time points after surgery (1 and 2 weeks post) between legs when 80% or more of muscle atrophy is occurring (37).

Primary Biochemical Outcome Measures.

To answer our study questions will be answered using an in vivo experimental design. **The procedure schedule can be referenced in Figure 1 (page 17, following a description of all study-related procedures and measures for Aim #1).**

Deuterium Oxide Ingestion Followed by Muscle Biopsies. Deuterium oxide (D_2O , i.e., heavy water) will be used to quantify chronic (days) muscle protein synthesis rates. D_2O will be ingested (50 ml) three times per day for 7 days leading up to TKA. During TKA surgery, a single biopsy will be obtained in the OR from each leg. Beginning on POD#1 and continuing through week 1 or week 2, subjects will continue ingesting 50 ml of D_2O twice daily. Bilateral biopsies obtained from each leg at 1 *or* 2 weeks post-TKA will be analyzed to determine muscle protein synthesis rates. All subjects will have a total of two biopsies from each leg, in a fasting state. This will allow us to determine the independent effects of supplementation on rates of muscle protein synthesis and breakdown (2H_2O) during the acute and sub-acute period.

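### The detectable sex-by-condition interactions in the power section are about 2.1 to 2.5 times too high for the stated completed samples, so the plan understates its sensitivity

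*Combined protocol and SAP*

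**What the plan says.** The Power analyses paragraph of the Data Analysis section states that "we have assumed a Type I error rate (α) of $.05$, two-tailed". The Power calculations list then gives main-effect figures for completed subjects:

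- **Aim 1, 20 per group** (10 per group for metabolic studies): "ESs of $d > 1.10$ with 85% power, assuming no pretest covariate", falling to "0.95 or 0.72 with pretest covariates of $r = .50$ or $.75$, respectively".
- **Aim 2, 40 per group:** "the proposed study can detect ESs of $d > .79$ with 85% power", falling to .68 and .52 for the same two correlations.

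Each item ends with a sex-moderation figure. For Aim 1 the effect is detectable if the "interaction accounts for at least 21% to 31% of the variance", and for Aim 2 if the "interaction accounts for at least 12% to 19% of the variance". In both cases the lower percentage belongs to r = .75 and the higher to r = .50. No formula, degrees of freedom or separate power is given for the interaction. The section then cautions that these tests probably lack power for some important effects, and says that effect size will be considered even without significance.

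**The concern.** A sex-by-condition interaction is a single contrast that uses every analysed subject. With 40 or 80 completers, thresholds of 21–31% and 12–19% of variance look far too high beside main-effect thresholds from the same subjects. Sex differences are formal questions in Aim 2 (2.2 and 2.5), and readers will judge the allowance for non-significant sex effects against these numbers. If they are more than twice too high, a null interaction in Aim 2 would be taken to exclude only very large effects, when the design is sensitive to considerably smaller ones.

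**Working it through.** **Inputs from the Data Analysis section.** Two-sided alpha .05; completers 20 and 40 per group, so N = 40 and N = 80; r = .75 or .50; printed minimum detectable effect sizes (MDES) as above. **Assumption:** the 85% power stated for the main effect also applies to the interaction.

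**1. Reproducing the printed percentages.** Take the printed covariate-adjusted MDES, set f² = d²/2, and compute share = f²/(1 + f²):

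| Aim, r | d | f² = d²/2 | share | printed | share with f² = d²/4 |
|---|---|---|---|---|---|
| 1, .50 | .95 | .451 | 31.1% | 31% | 18.4% |
| 1, .75 | .72 | .259 | 20.6% | 21% | 11.5% |
| 2, .50 | .68 | .231 | 18.8% | 19% | 10.4% |
| 2, .75 | .52 | .135 | 11.9% | 12% | 6.3% |

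All four printed values come back. For a 1-df contrast in a balanced design the conversion is f² = d²/4 (last column), so d²/2 doubles f².

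**2. The MDES that feed this step are also too large.** A two-sample t test at 85% power and no covariate gives d = 0.97 for 20 per group (printed 1.10) and 0.68 for 40 per group (printed .79). The printed values fit about 16 and 30 per group. This is why the d²/4 column still lies above the results in step 3.

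**3. Direct calculation.** Use the noncentral F test with 1 and N − 5 degrees of freedom and noncentrality f²·N. Solve for f² at 85% power, then apply the pretest covariate through (1 − r²), which is .4375 for r = .75 and .75 for r = .50. Two definitions of share are reasonable:

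- (a) f²(1 − r²) / [1 + f²(1 − r²)]
- (b) (1 − r²)·f² / (1 + f²), a share of total variance

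| N | f² | r = .75: (a), (b) | r = .50: (a), (b) | printed |
|---|---|---|---|---|
| 80 (Aim 2) | .115 | 4.8%, 4.5% | 8.0%, 7.7% | 12%, 19% |
| 40 (Aim 1, all subjects) | .237 | 9.4%, 8.4% | 15.1%, 14.4% | 21%, 31% |
| 20 (Aim 1, one biopsy time) | .514 | 18.4%, 14.9% | 27.8%, 25.5% | – |

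Example for N = 40, r = .50, definition (a): .237 × .75 = .178, and .178/1.178 = 15.1%.

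**4. Size of the gap, definition (a).** Aim 1: 21/9.4 = 2.2 and 31/15.1 = 2.1. Aim 2: 12/4.8 = 2.5 and 19/8.0 = 2.4. At the planned totals, power for the printed thresholds exceeds 99%.

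**5. Sensitivity, definition (a).** With about 12 model terms the results are 9.5–15.3% (N = 40) and 4.8–8.0% (N = 80). At 95% power they are 13.1–20.5% and 6.8–11.1%. Smaller alpha levels and 2- or 3-df interactions were also tried. No variant reproduces both aims at N = 40 and N = 80.

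**6. In treatment-effect units.** With four equal cells, a male-female difference in treatment effect of Δ SD accounts for Δ²/16 of total variance, so Δ = 4√share. For Aim 2, definition (b): 4√.045 = 0.85 and 4√.077 = 1.11. The printed 12% and 19% would be 1.39 and 1.74.

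**The case against.** **Aim 1 may refer to the metabolic subset.** The sentence before the Aim 1 interaction figure concerns cell and protein-synthesis outcomes with 10 subjects per condition. At one biopsy time the total is then 20, and definition (a) gives 18.4–27.8% at 85% power and 20.9–31.1% at 90%, which is close to the printed pair. This stands in part: an unqualified 8–15% would overstate sensitivity for those outcomes. It does not rescue the figures as a set. The match needs 90% power, which the plan does not state, and Aim 2 has no corresponding subset (N = 40 at 90% power gives 10.8–17.2%).

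**The cause is not documented.** A reader might infer that a per-group n was entered as the total, because the main-effect MDES fit 16 and 30 per group. The fit is imperfect. At 85% power, N = 16 gives 22.9% and 33.7%, not 21% and 31%, and the totals implied by the printed percentages are about 18 and 31–32. The d²/2 conversion fits all four values better, but it too is inference. Part of the gap also comes from the oversized main-effect MDES, so the two should not be counted as fully separate errors.

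**The practical consequence is small.** This is correct. A reader might take the finding to mean that power is inflated or the sample too small; the opposite holds. Nor does it refute the plan's caution about sex effects: a detectable difference of 0.85–1.1 SD in Aim 2 is about as large as the mean anticipated main effect (d = 1.01).

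**The plan may seem to contradict itself.** Under Study Aim #1, Randomization Assignments, the plan says "20/group, enough for sex comparison". That remark concerns the pooled questionnaire, activity, food-log, strength, volume and functional data, whereas the caution concerns some important effects. The emphasis differs, but the documents do not support calling it a contradiction.

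**Conclusion.** The four printed interaction thresholds are wrong for the completed samples beside which they stand. The gap is 2.4- to 2.5-fold in Aim 2 and 2.1- to 2.2-fold for Aim 1 outcomes analysed on all 40 subjects. The conclusion assumes a 1-df test, alpha .05 two-sided and 85% power, and is firmest for Aim 2. For Aim 1 it depends on which outcomes are meant. Attrition cannot explain the gap, because the sample sizes are given as completed subjects. The share-of-variance results do not depend on the sex split, which the plan does not give; the SD equivalents do. The error is conservative and leaves the sample size and the treatment comparison unchanged.

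**What to change.** In the Power calculations list:

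- Replace the Aim 2 interaction figures with about 5–8% (N = 80).
- Replace the Aim 1 figures with about 8–15% for outcomes analysed on all 40 subjects, and add about 18–28% (definition (a)) for metabolic outcomes analysed at a single biopsy time (N = 20).
- State N, power, degrees of freedom, formula and the definition of the variance share, and use one definition throughout.
- Add the equivalent male-female difference in treatment effect, about 0.85–1.1 SD in Aim 2 with balanced cells. Keep the caution about low power, which this supports.
- Recheck the main-effect MDES at the same time, since 20 and 40 per group give 0.97 and 0.68 without a covariate.

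The cost is a few numbers and two or three sentences. Trial conduct and enrolment are not affected.

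### Non-significant sex differences may be read as important from their size, with no interval or threshold, and the Aim 1 claim that 20 per group suffices for comparing the sexes conflicts with the power section

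*Combined protocol and SAP*

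**What the plan says.** Sex differences are listed study questions for Aim 2. Question 2.2 (Specific Aims) asks "Are there short-term sex differences on the above outcome measures", and question 2.5 asks the same of long-term mobility and quality of life. The Analysis of covariance paragraph names ANCOVA as the method for the research questions.

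Under Power calculations, the plan says a sex interaction is detectable if it explains 21% to 31% of the variance in Aim 1, or 12% to 19% in Aim 2. It adds that the interaction tests in both aims probably lack power for some effects that matter. From this it draws the consequence that "we will also consider the size of the effect, even if not statistically significant, as an indicator of potentially important sex-related differences". Data Analysis gives no cut-off, interval requirement or multiplicity provision for that reading.

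Under Study Aim #1, Randomization Assignments, the plan describes the pooled Aim 1 sample as "20/group, enough for sex comparison".

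**The concern.** Low power is a reason to trust a point estimate less. The plan gives it as the reason for looking at the point estimate when the test is not significant. Without an interval beside it, an interaction estimate of half an SD or more looks substantial next to an anticipated mean effect of about 1 SD, even when the data are compatible with no sex difference. The reading can be repeated over several functional tests, questionnaires and four post-operative visits.

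At stake is whether the reported answers to questions 2.2 and 2.5 show how uncertain they are. The Aim 1 remark adds to the problem, because it tells the reader that the smaller of the two samples is adequate for comparing the sexes.

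**Working it through.** **Inputs.** From Power analyses: "we have assumed a Type I error rate (α) of $.05$, two-tailed", and a mean anticipated effect of d = 1.01 for the physiological and functional outcomes. From Power calculations: 20 completers per group in Aim 1, 40 in Aim 2, 85% power, and pretest correlations r = .50 and .75. Assumed: equal numbers of men and women, because the documents give no sex ratio and mention stratification by sex for Aim 1 only.

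**The plan's own figures first.** The plan states "ESs of $d > 1.10$ with 85% power, assuming no pretest covariate" for Aim 1 and "the proposed study can detect ESs of $d > .79$ with 85% power" for Aim 2. A two-sample noncentral t calculation at 85% power gives 0.97 and 0.68. At the stated sample sizes, 1.10 and 0.79 have 92% and 94% power. The covariate reductions do follow, as d × √(1 − r²): 1.10 gives 0.95 and 0.73 (plan: "drops to 0.95 or 0.72 with pretest covariates of $r = .50$ or $.75$, respectively"), and 0.79 gives 0.68 and 0.52 (plan: "drops to .68 or .52 with pretest covariates of $r = .50$ or $.75$, respectively").

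The interaction percentages return only as D²/(D² + 4) with D = √2 × the plan's detectable effect: 31.1% and 20.6% in Aim 1, 18.8% and 11.9% in Aim 2. But √2 × that effect is the treatment effect detectable within one sex. The difference between the sexes needs 2 × that effect. A standard one-degree-of-freedom interaction test at 85% power gives a partial R² of 19.2% (N = 40) and 10.3% (N = 80). The results below do not use the plan's percentages.

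**Precision of the sex difference in EAA effect.** There are four sex-by-arm cells of c = 10 (Aim 1) or c = 20 (Aim 2), so SE = √(4/c) × √(1 − r²).
- Aim 1, r = 0: √(4/10) = 0.63. Aim 2, r = 0: √(4/20) = 0.45.
- The factor √(1 − r²) is 0.866 at r = .50 and 0.661 at r = .75.

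The largest non-significant estimate is SE × the t critical value. The chance of an apparent difference of size k with no true difference is 2 × [1 − Φ(k/SE)]. Detectable difference and power use the noncentral t.

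| Quantity (r = 0 / .50 / .75) | Aim 1 | Aim 2 |
|---|---|---|
| SE, SD units | 0.63 / 0.55 / 0.42 | 0.45 / 0.39 / 0.30 |
| Largest non-significant estimate, SD | 1.28 / 1.11 / 0.85 | 0.89 / 0.77 / 0.59 |
| Chance of at least 0.5 SD under no difference | 43% / 36% / 23% | 26% / 20% / 9% |
| Chance of at least 0.8 SD under no difference | 21% / 14% / 6% | 7% / 4% / 1% |
| Detectable with 85% power, SD | 1.95 / 1.69 / 1.29 | 1.36 / 1.18 / 0.90 |
| Power for a difference of 1.01 | 34% / 43% / 65% | 61% / 73% / 92% |

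The 0.5 and 0.8 SD cut-offs are assumptions, since the plan sets none.

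**Several outcomes.** The Function list under Aim 1 has eight tests, and Aim 2 drops the six-minute walk, leaving seven. Simulating seven equicorrelated null estimates at one visit, the chance that at least one reaches 0.5 SD is 61% to 78% at r = .50 and 34% to 49% at r = .75, as the inter-test correlation runs from 0.6 down to 0.

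**Sex split.** An unequal split widens the SE. In Aim 2 at r = 0, a 70:30 split gives √(2/28 + 2/12) = 0.49 instead of 0.45.

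**The case against.** The plan is more cautious than a quick reading suggests. It specifies a formal interaction test, admits that power is low, and says effect size will be looked at in addition, as an indicator. A reader might infer that sex differences will be declared on effect size alone; the text does not say that. A reader might also infer that most of what this reading picks out would be noise. That needs a cut-off and a prior for true sex differences, and the documents give neither. At 0.5 SD the null rate per outcome is below half in both aims.

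The size of the problem also depends on favourable inputs that are in the plan. The one functional-test correlation given is .78, for stair descent, so the r = .75 column may suit some Aim 2 outcomes best. Moreover, the sentence only adds estimates that are not significant. Removing the 5% that would be significant anyway leaves about 21% / 15% / 4% per outcome in Aim 2 at 0.5 SD, and the seven-test figures likewise include significant results. In the other direction, the plan's d is already scaled to a pretest-adjusted SD, so the r = 0 column may be the fair one to set against 1.01.

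The Aim 1 remark concerns pooled outcomes and speaks of comparing the sexes, not of an interaction, and the power section says power is short for some effects, not all. To call the remark simply false would therefore go too far. For muscle volume, r = .96 taken at face value brings the Aim 1 detectable difference to about 0.55 raw SD. That exception does not help questions 2.2 and 2.5, because Aim 2 has no MRI. Finally, the Aim 2 website text says the first part of the study was completed in 2016, so no Aim 1 design choice remains open.

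What stands is that estimates of considerable size can be non-significant here, and that nothing in the plan requires their uncertainty to be shown.

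**Conclusion.** The point holds as a reporting and interpretation gap. Looking at interaction effect sizes is reasonable; doing so without intervals, an exploratory label or a multiplicity caution is not. Non-significant estimates can reach 0.85 to 1.28 SD in Aim 1 and 0.59 to 0.89 SD in Aim 2, so chance differences can readily be flagged. How often depends on the assumed cut-off, the pretest correlation and the equal sex split.

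The Aim 1 adequacy remark conflicts with the power section and is unsupported for most endpoints. The Aim 1 detectable sex difference of 1.29 to 1.95 SD exceeds the mean anticipated effect of 1.01 at each r considered. Endpoints with very high pretest correlation, such as muscle volume, may be an exception.

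**What to change.** Keep the effect-size information and replace the sentence under Power calculations with: *Sex-specific EAA effects and the sex-by-condition interaction are reported with 95% confidence intervals for every outcome as exploratory, and no sex difference is claimed when the interaction interval includes zero.*

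Under Study Aim #1, Randomization Assignments, delete the adequacy remark or qualify it so that it agrees with the power section. State the detectable sex difference in SD units alongside the shares of variance, with the assumed sex split.

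The cost is a few sentences and no extra patients. Questions 2.2 and 2.5 become explicitly exploratory. Because Aim 1 is complete, the change there affects only how its results are interpreted.
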